
# B4. Approach

B4a. Theoretical Basis for Peer Mentoring

The Main Effect Model of Social Support posits that it is social relationships, and the support received from them, that are the primary drivers of improvements in both physical and mental health.99 The proposed peer mentoring intervention for African American women with SLE fits within a social support model that we hypothesize will influence this main effect by inducing downstream effects on health-related quality of life, mental well-being, and immune function, as it relates to disease activity. Within this model, we expect peer mentoring to reduce feelings of isolation and loneliness; provide culturally tailored, experiential, and evidence based education and information about accessing available health services; and promote behaviors that positively improve disease self-management, health-related quality of life, and disease activity.[86,100,101]

B4b. Study Overview. The Peer Approaches to Lupus Self-Management (PALS) study is a randomized controlled trial designed to examine whether a new, culturally tailored peer mentoring intervention improves disease self-management, indicators of disease activity, and health related quality of life (HRQOL) in African American women with systemic lupus erythematosus (SLE). African American women with active SLE will be recruited as mentees and peer mentors. We will recruit 300 mentees (150 mentored and 150 support group) and up to 60 mentors. As part of each wave, mentors (n=20) will be trained to deliver intervention content, prior to being paired with up to three mentees (n=50). The peer mentoring intervention will occur by twelve 60-minute telephone or video sessions carried out across the course of 24 weeks. In each wave, social support controls (n=50) will participate in a lupus support group

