**Data Collection Strategy** 

Data Collection Process/Schedule: Fourteen trained peer mentors will deliver the intervention in each wave and one full-time study coordinator (SC) will conduct screening, consent, enrollment procedures, and support group moderation. The primary method of data collection will be face to face interview. Mentees will be assessed at baseline, mid-intervention (3 months from baseline), immediately post-intervention (6 months from baseline), and 6 months post-intervention (12 months from baseline). Physical examination and laboratory evaluation will be achieved by in-person clinic visit when recent SLEDAI scores are not available in the database record of a given participant. Social support control participants will complete assessments on the same schedule as mentored participants. Given evidence that peer support may be just as beneficial to the supporters as it is to the person being supported, [118,119] mentors will be assessed on the same schedule as mentored and control participants, using the same tools.

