Randomization Procedure: Participants recruited for the mentored or control (support group) portion of the study will be randomized using a block randomization procedure to assure equal sample sizes in the mentored and control groups. Using a block size of 3, participants will be assigned to the appropriate treatment condition as they enroll in the study until the block is completed. Then the following 3 participants will be assigned based on the next block.[144] Once a patient is randomized and attends the first session, she will be entered into the study and included in the intent-to-treat analysis plan. Subjects will remain blinded to group allocation until after the completion of baseline assessment. The only members of the research team who will be aware of randomization assignment will be the Research Coordinator, and the statistical analyst in charge of randomization. Randomization will occur at the patient level. As such, we will take the following steps to minimize contamination between the two arms of the study: 1) patients in the intervention and control arms will be instructed not to share intervention materials with family members, friends, or other clinic patients; 2) patients will be given instructions not to disclose their treatment assignment to their assessment interviewers.

Data Management: Data will be captured via REDCap (a free, secure, web-based application) and overseen by a data management and analysis team comprising statisticians at MUSC. Data will be collected electronically in password-encrypted files. A part-time masters-level statistician will be responsible for data management. Data will be reviewed on a bimonthly basis and issues will be communicated to the project coordinators. In particular, outlying and inconsistent data values, as well as missing data, will be the targets of the data quality review.

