African Americans display the highest rates of lupus. Due to the exposure of African Americans to a unique trajectory of stressors throughout the life course, it may be critical to test peer mentorship as an alternative strategy to improve outcomes in this population. Given the success of the peer mentoring approach in other chronic conditions that disproportionately impact minorities, and its responsiveness to the needs of this unique population, this intervention could result in health improvements that have not been attainable with other interventions. This would significantly reduce disparities and have considerable public health impact.

In the United States, the highest lupus morbidity and mortality rates are among African American women. SLE affects approximately 1 in 250 African American women of childbearing age. Very few men are affected by the disease with a general ratio of 10 females to every 1 male with SLE.

Research Material & Data: Sources of research material include medical records, research questionnaires, and blood specimens. The data will be obtained for research purposes.

- 2. Linkages to Subjects: Participants will provide identifying information in addition to research data. Paper documents pertaining to this study will be stored in locked file cabinets in both the clinical center and the data management center, and data will be entered into secure, password-protected web databases developed for this study. A database of name, contact address, telephone number, and other research identification numbers will be stored separate from the study database, for purposes of audit by the MUSC IRB, if necessary. Access to study data will be limited to research personnel.
- 3. Collection of Data and Specimens:
- A. Personnel: A full-time research coordinator (RC) and part-time data coordinator (DC) will be responsible for consent, enrollment and data collection.

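### A block size of 3 cannot assure two equal arms, and the plan does not say how the next assignment is hidden from the coordinator who enrols

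*Combined protocol and SAP*

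**What the plan says.** The Randomization Procedure paragraph says that women will be "randomized using a block randomization procedure to assure equal sample sizes in the mentored and control groups". It then sets the rule: "Using a block size of 3, participants will be assigned to the appropriate treatment condition as they enroll in the study". The next three women are assigned from the next block, and randomization is at the level of the patient. The target in B4b (Study Overview) is "We will recruit 300 mentees (150 mentored and 150 support group) and up to 60 mentors", with 50 women per arm in each of three waves.

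On who knows what, the same paragraph says "The only members of the research team who will be aware of randomization assignment will be the Research Coordinator, and the statistical analyst" (the one who runs the allocation), and "Subjects will remain blinded to group allocation until after the completion of baseline assessment". It adds that "patients will be given instructions not to disclose their treatment assignment to their assessment interviewers".

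Staff duties appear in two other places:
- Collection of Data and Specimens, Personnel: "A full-time research coordinator (RC) and part-time data coordinator (DC) will be responsible for consent, enrollment and data collection".
- Data Collection Process/Schedule: "one full-time study coordinator (SC) will conduct screening, consent, enrollment procedures, and support group moderation".

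No section describes central or web-based assignment, sealed envelopes, or when an assignment becomes known to the person who enrols.

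**The concern.** There are two linked faults.

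First, the rule does not do what it is said to do. A completed block of 3 in two arms is never balanced, so equality depends on how blocks are composed and combined, and the plan is silent on both. A statistician could not build the list from this text.

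Second, assignment takes place as women enrol, and the same roles hold knowledge of assignments and control of entry. The Research Coordinator is named as aware of assignments and as responsible for consent and enrolment. The study coordinator screens, consents and enrols, and also moderates the control group, whose members she must therefore know. Entry leaves room for judgement: several mentee exclusions, such as acute decompensation of a chronic condition, call for an assessment, and the recruitment plan allows individual approaches if numbers lag. An enroller who can partly foresee the next assignment can, without intending to, influence who enters which arm. Selection bias of that kind cannot be fully repaired in the analysis.

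**Working it through.** **Plan's sample size.** Inputs from Power and Sample Size Justification: two-sided 0.05, 80% power, effect 0.35 SD, correlation 0.6 under compound symmetry, 20% inflation. For a change score, n per arm = 2 × ((1.960 + 0.842)/0.35)² × 2(1 − 0.6) = 128.14 × 0.8 = 102.5. Multiplying by 1.2 gives 123.0, which matches the stated 123 per group. The power figures below use the same variance.

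**Balance over the trial.** 300/3 = 100 blocks. Block composition is not stated, so this is an assumption: each block is 2:1 or 1:2 with probability 1/2. With K ~ Binomial(100, 0.5) blocks favouring one arm, the arm difference is d = 2K − 100.
- P(d = 0) = P(K = 50) = 0.080.
- SD of d = 2 × √25 = 10.
- P(|d| ≥ 10) = 0.368; P(|d| ≥ 20) = 0.057.

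A different assumption, exactly 50 blocks of each type, would give 150:150.

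**Balance within a wave.** 100 women make 33 complete blocks plus one woman. A 50:50 split needs a difference of ±1 after 33 blocks and a last woman who offsets it: (0.1358 + 0.1358) × 1/2 = 0.136.

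**Power.** N = 300, 20% loss, change-score variance 0.8:
- 150:150 leaves 120 and 120. SE = √(0.8 × (1/120 + 1/120)) = 0.1155; 0.35/0.1155 − 1.96 = 1.071; power 85.8%.
- 160:140 leaves 128 and 112. SE = √(0.8 × (1/128 + 1/112)) = 0.1157; 0.35/0.1157 − 1.96 = 1.064; power 85.6%.

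B4c (Scientific Rigor) pairs a correlation of 0.7 with AR(1), under which the correlation between baseline and 12 months decays. With 0.49 (two steps) the powers are 76.6% and 76.4%. The level changes, but the cost of imbalance does not.

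**Guessing the next assignment.** Assume the enroller knows the block size and sees past assignments. The six mixed sequences are AAB, ABA, BAA, ABB, BAB and BBA.
- First place: best guess correct 1/2.
- Second place: 2/3.
- Third place: certain if the first two agree (probability 1/3), otherwise 1/2, so 1/3 + 2/3 × 1/2 = 2/3.

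The average is (1/2 + 2/3 + 2/3)/3 = 0.611. The share that is certain is (1/3)/3 = 0.111.

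For comparison, with past assignments visible:

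| Scheme | Best guess correct | Certain |
|---|---|---|
| Blocks of 3, randomly 2:1 or 1:2 | 61% | 11% |
| Fixed blocks of 4 | 71% | 33% |
| Random blocks of 4 or 6, only the set of sizes known | 69% | 6% |
| Past assignments hidden | 50% | 0% |

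The 4-or-6 row comes from 3,000 simulated waves of 100; the other rows are exact.

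**The case against.** The best defence on balance is that the text is incomplete rather than wrong. The 3 may be a slip, or the list may hold 50 blocks of each type. Either is possible, but an equal mix is a further rule that the plan does not state, and the paragraph repeats the number three. It has to be corrected in either case.

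On concealment, an analyst is in charge of randomization, and women do not learn their group until baseline is done. Nor does the plan say when the Research Coordinator becomes aware; the moderator may learn who the controls are only when sessions start. This stands to the extent that the guessing rates are conditional on past assignments being visible during enrolment. It does not fill the gap, since neither safeguard addresses the enroller.

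A reader might infer more than the documents support:
- **A 200:100 trial**, with every block 2:1 the same way. This contradicts the stated equal arms and the 150:150 target.
- **Whole blocks sent to one arm.** This contradicts randomization at patient level.
- **Follow-up outcomes collected by staff who know the arm.** The documents do not establish this. Blinding is claimed in B4c, women are asked not to tell their interviewers, and the data coordinator is not on the list of those aware. What stands is that the role descriptions do not fit together.

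**Conclusion.** The concern holds on two counts. The block rule cannot deliver its stated purpose and cannot be implemented as written, and concealment from the enroller is not described. Both need correcting, because neither can be put right after enrolment.

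The size depends on an unstated composition. Under random 2:1 or 1:2 blocks, the chance of 150:150 is 8%, the chance of a difference of 10 or more is 37%, and the chance of 50:50 in a wave of 100 is 14%. The loss of power is about 0.2 percentage points at 160:140, so power is not the reason to act. The reason is exposure to selection bias, with 61% of assignments guessable and 11% certain if past assignments are visible. No amount of bias and no type I error figure is claimed.

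Who collects follow-up outcomes is a separate, lower-priority clarification. Methods for Aim 2 has the study coordinator coordinate questionnaires; the Personnel paragraph gives data collection to the research and data coordinators; the Randomization Procedure limits awareness to the Research Coordinator and the analyst; and the safety monitoring text places study coordinators at both data collection and intervention activities. Interviewer influence on LUP-QOL and PAM is possible but not shown.

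**What to change.** 1. **List.** Replace the block of 3 with permuted blocks of randomly varying even size, for example 4 and 6, stratified by wave, with sizes withheld from enrolling staff. At woman 100 of a wave the open block holds 0, 2 or 4 women, so the arms differ by at most 2 per wave and at most 3 × 2 = 6 overall.
2. **Concealment.** Have the statistician hold the list and release each assignment through REDCap only after eligibility, consent and baseline are complete. Keep past assignments from whoever consents. This must accompany step 1: if past assignments stay visible, even blocks raise the best-guess rate from 61% to about 69%, although certain assignments fall from 11% to 6%.
3. **If one coordinator must both enrol and moderate.** Assignments could be released in batches once the batch's baselines are done. A block left open between batches stays partly predictable for the next batch. The gap from baseline to first session also lengthens. Sessions run for 24 weeks and visits are timed from baseline, so with six months taken as 26 weeks there are only about 2 weeks to spare. A longer wait would move the 6-month visit into the intervention period for early enrollees.
4. **Clarification.** Reconcile the four role descriptions named in the verdict, and state whether Research Coordinator and study coordinator are one role. Have follow-up LUP-QOL and PAM self-completed in REDCap, as already allowed for women outside MUSC, or collected by existing staff not aware of assignment.

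The cost is a new list, a REDCap release step and some reallocation of duties, with no extra participants. The data coordinator is part-time, so moving interviews to that role needs a workload check. Women will still know their own arm when they report outcomes, and these changes do not alter that.

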# Overview of Statistical Analysis Plan

Univariate descriptive statistics and frequency distributions will be calculated as appropriate for all variables for the total sample. Descriptive analysis will be presented as percentages (with 95% confidence intervals [95% CI]) for categorical variables, and either means (±Standard deviation) with 95%

CI or medians (with interquartile range) for continuous and ordinal variables on the biological indicators of disease activity, as appropriate, based on distributional assumptions. These analyses will provide descriptors of the respective parameters in the study population and will also be used to identify departures from distributional assumptions for proposed procedures. If departures are identified, appropriate transformations of data will be applied, or alternative analysis procedures (e.g., semi-parametric or nonparametric) will be used.

AIM 1: Determine the efficacy of a peer mentorship intervention in African American women with SLE on disease self-management and HRQOL. Analyses for Aim 1 will focus on estimation of efficacy as determined by: (a) change in quality of life; and (b) change in self-management. Estimates of effect sizes for outcome variables will be reported as point estimates (mean differences between pre-post measures. as appropriate) and interval estimates (95% CI) with two-sided p-vales denoting statistical significance to provide an indication of the presence of a clinically important treatment effect. [145,146] A p-value of 0.05 will be considered to be statistically significant. After studying the distributions of baseline characteristics. we will use a generalized linear mixed model regression model to determine if the intervention will produce a greater change in the main outcomes from baseline. This model will include time, treatment (along with their interaction), and covariates (including the amount of intervention received, demographic factors, medications, coping, depression, stress, anxiety, health literacy, trust, and social support) as fixed-effects. Using the amount of intervention, which is measured as an aggregate number of sessions completed or hours of interaction as a covariate would allow us to study the dose response. In the generalized linear mixed model (GLMM), we will use different link functions depending on the assumed distribution of the response variable. For binary outcomes, we will use logit link and for count outcomes we will use log link under a poisson or negative binomial distribution. For example, for the a given quality of life variable, HRQOL measured at baseline, month 3 and month 6, we will include intervention group, time, and time X intervention as the primary independent variables in the basic (unadjusted) model, and covariates that are not balanced at randomization (or a propensity score based on these covariates) will be added in the subsequent (adjusted) model to adjust for the possible confounding effect of these variables. Unadjusted and covariate-adjusted least squares means for each outcome variable will be compared at the primary time point (month 12) and at intermediate secondary time point (month 6) using appropriate model contrasts and the Tukey-Kramer adjustment for multiple comparisons for the secondary time points. These contrast comparisons, along with corresponding 95% CI, will provide estimates of the difference in outcome means (effect sizes) for the hypothesized comparisons.

AIM 2: Determine the impact of a peer mentorship intervention in African American women with SLE on clinical indicators of disease activity and clinical profile that indicates success of the intervention. Analyses for Aim 2 will focus on estimation of efficacy as determined by: change in disease activity of ≥4 point reduction from baseline in SLEDAI score, in concordance with the accepted SLE Responder Index (SRI).[147] For comparative statistical assessments, the two groups will be compared using a generalized linear mixed models (GLMM) approach.[148] This approach allows for measurement of participants at different time points, missing data under the assumption of missing at random (MAR), and can also account for the effect of correlated longitudinal measurements within participants. In addition, GLMM accommodates a wide range of distributional assumptions such as dichotomous (e.g. binomial), count (e.g. Poisson), continuous (e.g. Gaussian), and categorical or ordinal outcomes. Additionally, outcomes that are measured longitudinally (at 6 and 12 months) will have intervention group, time, and time-by-intervention group as primary independent variables in the model. Additional adjustment covariables will be added to the model in a second set of analyses, when indicated. The magnitude of between intervention differences in outcome variables (effect sizes) at each time point will be estimated using appropriate contrasts in the corresponding GLMM models. We will then perform a responder analysis to develop a profile of the clinical and laboratory characteristics that predict success of the intervention. For this, a multivariate regression logistic regression model where the outcome is success (/failure) and the difference in the clinical (SLEDAI components) levels over time are independent variables. We will use model selection approaches such as the all subsets selection, to identify the important clinical and laboratory features in the presence of others. As much as the data allows, we will also consider interactions of the SLEDAI components. As an alternative to logistic regression, we will also consider other approaches such as the CART, or logic forest to efficiently identify the clinical and laboratory characteristics that predict intervention success.

Secondary analyses of process measures: Important process measures will include recruitment, session attendance/dropout proportions and participant satisfaction. We will use 95% confidence intervals (CI) for proportions to estimate the proportion of participants who agree to participate out of the number who are initially approached, the proportion who are compliant with the treatment protocol, and the proportion who exit the study prematurely (drop out). In addition, frequency distributions describing the participants' reasons for noncompliance and discontinuation of study participation will be developed. We will also evaluate patient satisfaction with the peer mentoring intervention using a likert-type satisfaction scale and will determine the proportions (along with CI) within the categories. For continuous process measures (e.g. treatment credibility, treatment adherence, peer mentoring phone sessions and attrition), frequency distributions and the median and mean responses (with 95% CIs) will be obtained.

Exploratory analyses to determine the role of mediators and moderators on outcomes and obtain estimates of the effect of the intervention on mentors: Analysis for exploratory aims will focus on change scores over time for potential mediator and moderator variables related to identified unmet needs unique to African American women with SLE, including: (a) Anxiety; (b) Depression; (c) Stress; (d) Coping; (e) Health Literacy; (f) Trust; (g) Social Support; and (h) Patient centered care. Differences between baseline and post-baseline measurements will be tested with the Wald test in the GLMM model. As described for Aim 1, estimates of effect sizes for the outcome variables will be obtained via 95% confidence intervals (CI) to provide an indication of the presence of a clinically important treatment effect. Individual treatment change scores (pre-post) will be estimated via 95% CI (adjusting for clustering).[145,146] Since the intervention is designed to improve outcomes in mentees, we will not have power to test the efficacy of the intervention in the mentors, but will explore the effect of the intervention on the mentors using the same analytical methods.

Missing data: We will handle missing data using several techniques including multiple imputation and maximum likelihood,[149] and latent class based multiple imputation.[150] Missing data mechanisms will be examined using both univariate and multivariate methods. We will check for missing at random (MAR) by creating a missing indicator for each missing variable and study the predictors of missingness using logistic regression. If any of the fully observed covariates or outcomes become significant in the missing data model then we will use methods for MAR if we do not have any reason to believe that the missing data mechanism is not at random.

Mid-point Analyses for the protection of participants: In an effort to protect both mentors and mentees from potential deleterious effects of mentoring, a mid-point (interim) analysis will be undertaken to assess safety using 3-month post-intervention data. If mentored participants have worsened beyond a threshold, we will stop the trial for ethical concerns. For instance, if the lower confidence limits based on 95% confidence interval at the midpoint, for any one of the variables, namely depression, anxiety, and/or disease activity, is larger than 50% compared with their baseline measure, the trial will be terminated. Similarly, mentors will be monitored for depression, anxiety, and disease activity and if a worsening trajectory is observed at mid-point analyses, they will be removed from the study.

AIM 3: Determine the cost and cost-effectiveness of a peer mentorship intervention on disease self-management, disease activity, and HRQOL, in African American women with SLE.

The cost of the intervention will be compared to the outcomes of the intervention 12 months post baseline. In order to compare with previous lupus studies,[151,152] Quality adjusted life years (QALYS) will be calculated for intervention and control groups based on the SF36 outcome which will be measured 12 months post baseline. The calculation will be based on an established peer reviewed method.[153] Measuring QALYS gained relative to cost of the intervention is the preferred outcome method for the American College of Physicians (ACP).[154]

Using QALYs, the incremental cost-effectiveness ratio (ICR) can be calculated as: (QALYintervention-QALYcontrol)/(Costintervention-CostControl). The ICR can then be compared with the ICRs for previous lupus interventions. We will take the perspective of the provider, insurer and patient. All three are affected in the hospitalization charges since insurers pay part and patients will pay part of the charges. In addition to the main cost-effectiveness outcome of QALY and the ICR, costs of the

intervention can be compared with any changes in MUSC health services utilization costs for emergency department, inpatient and outpatient care for the intervention relative to the control group. In addition to a comparison of intervention cost with average difference between MUSC costs for intervention and control group 12 months post baseline, generalized linear cost models can be estimated to examine the association of the treatment with MUSC health services costs while adjusting for patient demographics (age, gender, race/ethnicity, co-morbidities) and clinical outcomes. MUSC does not provide cost information, only charges. In addition we will estimate the impact on work loss and income by estimating the changes in days lost to illness and income based on values provided by participants. We will use the year for which the hospital charge and income data is reported and adjust for inflation as appropriate using the US Department of Labor Consumer Price Index. Inpatient and outpatient MUSC costs will be compared separately and together between the control and intervention groups. Bootstrapping methods will be used to conduct sensitivity analyses for all cost models. Sensitivity analysis will be performed by estimating a separate MUSC health services cost model while adjusting for each clinical outcome to insure robust results regarding the marginal effect of the treatment on MUSC health services costs. Park tests will be conducted to determine the best fit for the cost data in specifying the generalized linear model. In the event of many zero values, a two-part model will be used to first examine the association of the treatment with the likelihood of any MUSC costs and then the conditional generalized linear cost model, conditional on having non zero MUSC cost value for the patient. The ICR will be reported as a single ratio with no uncertainty attached to it. Therefore, standard statistical characteristics such as confidence intervals or hypothesis test to compare it to an a priori ICR from another study are not applicable. We will calculate the ICR and a clinically relevant interpretation of the outcome will be p Human Subjects Involvement and Characteristics. The Peer Approaches to Lupus Self-Management (PALS) study is a randomized controlled trial designed to examine whether a new, culturally tailored peer mentoring intervention improves disease self-management, indicators of disease activity, and health related quality of life (HRQOL) in African American women with systemic lupus ervthematosus (SLE). African American women with active SLE will be recruited as mentees and peer mentors who are considered competent in the management of their condition will be identified and recruited to provide modeling and reinforcement to participants. We will recruit mentees for 300 observations (150 mentored and 150 support group) and up to 60 mentors. Mentees and mentors will be primarily recruited from the longitudinal web-based SLE database at the Medical University of South Carolina (MUSC) in three cohorts. As part of each cohort, mentors (n=20) will be trained to deliver intervention content, prior to being paired with up to three mentees (n=50). The peer mentoring intervention will occur by twelve 60minute telephone or video sessions carried out across the course of 24 weeks. In each cohort, social support controls (n=50) will participate in a lupus support group created for this project, on the same schedule as peer mentoring sessions. All participants (mentees, mentors, and social support controls) will be assessed using validated measures of patient reported outcomes and biological indicators of disease activity at baseline, mid-intervention (3 months from baseline), immediately post-intervention (6 months from baseline), and 6 months post-intervention (12 months from baseline). For each cohort, outcomes for mentees randomized to the mentored group will be compared with the outcomes of mentees randomized to the social support control group. A booster session will be incorporated for mentored participants at 3 months post-intervention to encourage retention.

Inclusion criteria FOR MENTEES include: 1) African American race/ethnicity and female gender; 2) clinical diagnosis of systemic lupus erythematosus (SLE) from a physician; 3) 18 years of age or older; 4) able to provide informed consent and take part in ongoing assessment/evaluation activities (self-reported questionnaires, interviews); 5) able to commit to duration of study (12 months); and 6) able to communicate in English. Exclusion criteria FOR MENTEES include: 1) cognitive impairment; 2) active alcohol or drug abuse/dependency; 3) acute decompensation of chronic conditions precluding participation; 4) conditions that preclude participation in assessments (e.g. blindness or deafness); 5) terminal illness or life expectancy less than 18 months as evaluated by physician; and 6) current enrollment in an interventional study or trial that could affect quality of life outcomes and/or participation in one of the PI's prior behavioral trials.

Inclusion criteria FOR MENTORS include: 1) African American race/ethnicity and female gender; 2) clinical diagnosis of systemic lupus erythematosus (SLE) from a physician; 3) 18 years of age or older; 4) able to provide informed consent and take part in ongoing assessment/evaluation activities (self-reported

questionnaires, interviews, observation, activity logs); 5) able to commit to duration of study (12 months); 6) able to communicate in English; 7) disease duration > 2 years; 8) able to attend scheduled training sessions; 9) willing to provide one-on-one support to up to three African American women with SLE; and 10) PI determination of competence, maturity, emotional stability, and verbal communication skills after overall assessment during screening interview and training. Exclusion criteria FOR MENTORS include: 1) cognitive impairment; 2) active alcohol or drug abuse/dependency; 3) acute decompensation of chronic conditions precluding participation; 4) conditions that preclude participation in assessments (e.g. blindness or deafness); and 5) terminal illness or life expectancy less than 18 months as evaluated by physician. rovided similarly to other studies in the literature.[155,156]

African Americans display the highest rates of lupus. Due to the exposure of African Americans to a unique trajectory of stressors throughout the life course, it may be critical to test peer mentorship as an alternative strategy to improve outcomes in this population. Given the success of the peer mentoring approach in other chronic conditions that disproportionately impact minorities, and its responsiveness to the needs of this unique population, this intervention could result in health improvements that have not been attainable with other interventions. This would significantly reduce disparities and have considerable public health impact.

In the United States, the highest lupus morbidity and mortality rates are among African American women. SLE affects approximately 1 in 250 African American women of childbearing age. Very few men are affected by the disease with a general ratio of 10 females to every 1 male with SLE.

Research Material & Data: Sources of research material include medical records, research questionnaires, and blood specimens. The data will be obtained for research purposes.

- 2. Linkages to Subjects: Participants will provide identifying information in addition to research data. Paper documents pertaining to this study will be stored in locked file cabinets in both the clinical center and the data management center, and data will be entered into secure, password-protected web databases developed for this study. A database of name, contact address, telephone number, and other research identification numbers will be stored separate from the study database, for purposes of audit by the MUSC IRB, if necessary. Access to study data will be limited to research personnel.
- 3. Collection of Data and Specimens:
- A. Personnel: A full-time research coordinator (RC) and part-time data coordinator (DC) will be responsible for consent, enrollment and data collection.
- B. Data Collection Schedule: At the baseline visit, the RC will give detailed explanation of the study, the reimbursement schedule, and obtain consent. Participants will provide a blood sample, if necessary, and complete a questionnaire that captures demographics, health literacy, coping, disease activity, disease self-management, anxiety, depression, perceived stress, social support, trust, patient centered care, perceived control, perceived discrimination, spirituality, and quality of life. The RC will review study goals, establish the schedule of study sessions, obtain contact information (primary and alternate telephone numbers), and receive study materials. After the baseline assessment, follow-up assessments will be conducted at 6 months (questionnaire only) and 12 months (questionnaire and blood collection). As much as possible, research visits will be scheduled on the same day as their clinic visit. Mentors and mentees will be on the same schedule of data collection, regardless of whether a mentor has assigned mentees after their enrollment.

Potential risks to mentees and mentors include: 1) discomfort, bruising, or scarring from venipuncture, 2) possible violation of the patient's privacy, 3) discomfort with questions on the research questionnaire, and 4) psychological distress. Additional risks to mentors specifically include: 1) discomfort with interactions with mentees and 2) feeling overwhelmed. Details on how these risks will be minimized are discussed under adequacy of protection against risks below.

Confidentiality: This will be maintained by keeping participant folders in locked file cabinets in the research center. Only participants' unique identification numbers will be recorded in folders and on data forms. The database will remain on the MUSC computer system that use unique ID numbers, rather than names, and will be password-protected. To further ensure confidentiality, participants will be provided

with a basic phone and calling/texting plan for the duration of the study for mentoring interactions so that personal phones are not used.

Recruitment and Informed Consent. All African American lupus patients who indicate willingness to participate and meet the inclusion criteria of the study will be invited to participate in data collection. Informed consent will be sought from each participant for participation in intervention and data collection activities. Participants will be encouraged to ask any questions they have regarding the procedures. There will be no coercion to participate or prejudice against those who choose not to take part in the study. We will submit an application to the Medical University of South Carolina Institutional Review Board for approval of study procedures and the informed consent protocol. Study activities will not take place prior to IRB approval.

After obtaining approval from the IRB, we will obtain a list of potential mentors from MUSC rheumatologists and the full list of female African American SLE patients enrolled in the web-based SLE database who have consented to future contact to be contacted as mentees. We will mail out recruitment letters that will explain the study and provide participants a number to call if they are interested in participating. Participants who call and indicate interest in the study will be contacted by telephone to conduct a pre-screening assessment. If eligibility criteria are met the screening/enrollment visit will be scheduled. Additional recruitment strategies will include invitations to other academic medical centers with eligible patient populations, the identification of local SLE support group members who have emerged as natural helpers, referrals from other rheumatologists and arthritis health professionals, and outreach to the local chapters of the Lupus and Arthritis Foundations by letter and telephone.

